7. To estimate the relative risk of **mCM** in live and non-live offspring from women with moderate/severe SLE exposed to anifrolumab anytime during pregnancy compared to women with moderate/severe SLE exposed to SOC and unexposed to anifrolumab anytime during pregnancy
8. To describe and estimate the risk of **adverse pregnancy outcomes** separately (ectopic pregnancy, spontaneous abortion, elective termination of pregnancy, stillbirth, infections requiring hospitalisation during pregnancy, emergency caesarean section) and as a composite of foetal loss (composite of spontaneous abortion, ectopic pregnancy, elective termination of pregnancy, and stillbirth) in pregnancies from
 - a. women with moderate/severe SLE exposed to anifrolumab anytime during pregnancy
 - b. comparable population of women with moderate/severe SLE exposed to SOC and unexposed to anifrolumab anytime during pregnancy
9. To estimate the relative risk of **adverse pregnancy outcomes** separately (ectopic pregnancy, spontaneous abortion, elective termination of pregnancy, stillbirth, infections requiring hospitalisation during pregnancy, emergency caesarean section) and as a composite of foetal loss (composite of spontaneous abortion, ectopic pregnancy, elective termination of pregnancy, and stillbirth) in pregnancies from women with moderate/severe SLE exposed to anifrolumab anytime during pregnancy compared to women with moderate/severe SLE exposed to SOC and unexposed to anifrolumab anytime during pregnancy
10. To describe and estimate the risk of **adverse birth outcomes** (preterm birth, small for gestational age (SGA)) in live offspring from
 - a. women with moderate/severe SLE exposed to anifrolumab anytime during pregnancy

- b. comparable population of women with moderate/severe SLE exposed to SOC and unexposed to anifrolumab anytime during pregnancy
11. To estimate the relative risk of **adverse birth outcomes** (preterm birth, SGA) in live offspring from women with moderate/severe SLE exposed to anifrolumab anytime during pregnancy compared to women with moderate/severe SLE exposed to SOC and unexposed to anifrolumab anytime during pregnancy

Exploratory objectives

12. To describe and estimate the risk of **adverse outcome related to infant growth** up to one year of age of live offspring from
 - a. women with moderate/severe SLE exposed to anifrolumab anytime during pregnancy

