
Secondary objective 5c-d, 8 & 9
 
Exploratory objective 13 & 14
	
pregnancy outcomes, separately and as a composite of foetal loss
 
Estimate relative risk of select pregnancy loss outcomes (composite of spontaneous abortion and stillbirth), adverse pregnancy outcomes, separately and as a composite of foetal loss.
 
Describe cohort demographic and clinical characteristics.
 
Among pregnant women
			
 Ectopic pregnancies (except for ectopic pregnancy outcome)

Primary objective 3 & 4
 
Secondary objective 5c-d, 8 & 9
 
Exploratory objective 13 & 14
	
Describe and estimate risk of select pregnancy loss outcomes (composite of spontaneous abortion and stillbirth), adverse pregnancy outcomes, separately and as a composite of foetal loss.
 
Estimate relative risk of select pregnancy loss outcomes (composite of spontaneous abortion and stillbirth), adverse pregnancy outcomes, separately and as a composite of foetal loss.
 
Describe cohort demographic and clinical characteristics.
 
Among pregnant women
	
Unexposed study population
	
pregnancy_unexp
	
EXCLUSION:
 
 Pregnancies exposed at any time to anifrolumab (+16 weeks prior to LMP2) (see Section 9.3.1) Ectopic pregnancies (except for ectopic pregnancy outcome)

Secondary cohort birth (birth_exp+ birth_unexp)
				

Secondary objective 5c-d, 10 & 11
	
Describe and estimate risk of adverse birth outcomes.
 
Estimate relative risk of adverse birth outcomes.
 
Describe cohort demographic and clinical characteristics.
 
Among live offspring
	
Exposed study population
	
birth_exp
	
INCLUSION:
 
 Pregnancies exposed at any time to anifrolumab (+16 weeks prior to LMP2) Pregnancies with linkage mother-offspring within the study time period

Objective	Main features	Input Cohort/ Population	Sub-cohort Abbreviation	Additional criteria to be applied to the input Cohort/ Population

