- **Spontaneous abortions**¹²: unintended loss of an intrauterine pregnancy which is less than 22 weeks of gestation for the European data sources (40); less than 20 weeks for the USA data sources (64);
- **Ectopic pregnancy:** occurs when a fertilised egg implants outside of the uterus, usually in one of the fallopian tubes.
- **Elective termination of pregnancy:** is defined as the intentional termination of pregnancy at any time in gestation for any reason. When possible, reasons for elective termination are captured and classified as elective termination of pregnancy for foetal anomaly or for other reasons.
- **Stillbirth**¹³: unintended foetal death occurring at or after 22 weeks of gestation for the European data sources (78); at or after 20 weeks for the USA data sources (64).
- **Composite of foetal loss:** will be defined as the presence of at least one of the following: spontaneous abortion, ectopic pregnancy, elective termination of pregnancy and stillbirth.
- **Infections requiring hospitalisation during pregnancy:** infections requiring hospitalisation during pregnancy will be considered as the occurrence of the first event of a hospitalisation for an infection diagnosis, as primary diagnosis. The list of the infections considered, and their respective ICD-10 codes are presented in [Table 24](#).
- **Emergency caesarean section:** surgical procedure involving the incision of the walls of the abdomen and uterus for delivery of an offspring that occurs when vaginal delivery is

¹⁴ Specific outcome censoring rules will be applied. For spontaneous abortion and ectopic pregnancy there will be outcome specific end of follow-up dates. For spontaneous abortion outcome specific end of follow-up will be 22 weeks of gestation as for the ectopic pregnancy end of follow-up will be 16 weeks of gestation further details will be specified in the SAP.

¹⁵ To maximize the capture of non-live births for spontaneous abortion, elective termination, and stillbirth, an exhaustive list of codes related to pregnancies as well as to outcomes will be used, i.e., every code will be included.

discontinued due to unexcepted complications during labour, such as the occurrence of foetal distress (105).

Adverse birth outcomes

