9.5.1.1 Assumptions used for the sample size and power calculations

To estimate the number of anifrolumab exposed SLE pregnancies and the expected number of primary study outcome events in data sources that would be eligible for the analysis in this study, the following assumptions were used:

- **A prevalence of 7% for MCM outcome.** Prevalence of MCM in pregnancies in women with moderate-to-severe SLE was estimated based on a literature search. Among moderate/severe SLE patients exposed to belimumab, birth defect prevalence estimates of 5.6% to 21.7% were observed in post hoc summary of clinical studies and a prospective

pregnancy registry, respectively (86) A prevalence of 6.4% of congenital malformations was observed in renal SLE pregnancies (51) These proxy estimates of MCM in moderate-to-severe SLE align with the observed population based prevalence estimates ranging from 7.4% to 13.6% (114) among women diagnosed with SLE (117).

- **A prevalence of 20% for the composite of select pregnancy loss outcomes (composite of spontaneous abortion and stillbirth).** Prevalence of the composite outcome of select pregnancy loss (spontaneous abortion and stillbirth) in moderate-to-severe SLE pregnancies ranged from 15.3% to 30% (51, 81, 86). For the individual outcomes, the prevalence estimates ranged from 1.8% to 3.7% for stillbirths (51, 103, 120), and the prevalence estimate was 16% (12.1% to 19.9%) for spontaneous abortions (103). Based on the intended objective to evaluate embryo-foetal loss, a composite outcome of spontaneous abortion and stillbirth has been used.
- **Proportion of SLE pregnancies occurring in women with moderate-to-severe disease of 50%.** There is limited information on the proportion of SLE pregnancies that occur in women with moderate-to-severe disease. The proportion of moderate-to-severe disease at the time of diagnosis among the general SLE population is estimated to be 50% (66, 80). Literature regarding medication patterns for SLE pregnant women suggests that 40-45% use immunosuppressors and/or biologics, which may be a proxy indicator of moderate/severe disease (12, 67). Thus, in this study, an assumption of 50% was used.

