To estimate the relative risk of mCM in live and non-live offspring from the mothers who had moderate/severe SLE and were exposed or unexposed to anifrolumab during pregnancy (study objective 7), the crude and adjusted RRs (with corresponding 95% CI) will be estimated using the *mCM* cohort. The crude RR and its 95% CI will be estimated using a regression model as specified in Section [9.7.1](#). The adjusted RR and its 95% CI will be estimated using the same regression model following an appropriate PS adjustment method as described in Section [9.7.1](#).

Objective 8

The analysis to describe and estimate the risk of adverse pregnancy outcomes (as defined in Section [9.3.2](#)) in all pregnancies from the mothers who had moderate/severe SLE and were exposed or unexposed to anifrolumab during pregnancy (study objective 8) will be performed using the *pregnancy* cohort (as defined in Section [9.2.2](#)). The crude and adjusted cumulative incidence (with corresponding 95% CI) of the adverse pregnancy outcomes (as defined in Section [9.3.2](#)) will be calculated for cases where the mother was exposed to anifrolumab during pregnancy and for cases where the mother was unexposed to anifrolumab during pregnancy. The crude cumulative incidence (i.e., risk) will be calculated as the total number of each adverse pregnancy outcome (as defined in Section [9.3.2](#)) divided by the total number of pregnancies. The adjusted cumulative incidence (i.e., risk) will be estimated following PS adjustment.

Objective 9

To estimate the relative risk of adverse pregnancy outcomes (as defined in Section 9.3.2) in pregnancies from the mothers who had moderate/severe SLE and were exposed or unexposed to anifrolumab during pregnancy (study objective 9), the crude and adjusted RR (with corresponding 95% CI) will be estimated using the *pregnancy* cohort (as defined in Section 9.2.2). The crude RR and its 95% CI will be estimated using a regression model as specified in Section 9.7.1. The adjusted RR and its 95% CI will be estimated using the same regression model following an appropriate PS adjustment method as described in Section 9.7.1.

Objective 10

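### Table 5 removes ectopic pregnancies from the cohort used for the foetal-loss composite, although ectopic pregnancy is one of that composite's four defined components

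*Protocol*

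**What the plan says.** Table 5 in Section 9.2.2 defines the pregnancy cohort, with an exposed and an unexposed row. Both rows carry the line "Ectopic pregnancies (except for ectopic pregnancy outcome", and no other outcome is exempted. The same rows assign this cohort to Objectives 8 and 9, covering "pregnancy outcomes, separately and as a composite of foetal loss".

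In Section 9.3.2 the foetal-loss composite "will be defined as the presence of at least one of the following: spontaneous abortion, ectopic pregnancy, elective termination of pregnancy and stillbirth". Section 8.1 words Objectives 8 and 9 the same way: "as a composite of foetal loss (composite of spontaneous abortion, ectopic pregnancy, elective termination of pregnancy, and stillbirth) in pregnancies from".

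Section 9.7.3 runs Objectives 8 and 9 in the pregnancy cohort of Section 9.2.2, with the count of each outcome "divided by the total number of pregnancies". Table 3 in Section 9.1 gives the population for the composite, and for every other adverse pregnancy outcome, as all pregnancies.

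**The concern.** The cohort definition and the outcome definition cannot both be followed. The composite needs ectopic events, but the only cohort it is analysed in has had them removed. The exemption names the ectopic outcome alone, and Table 5 itself treats the separate outcomes and the composite as different analyses.

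The consequences fall on secondary Objectives 8 and 9:

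- The published foetal-loss risk and risk ratio would describe a three-component endpoint under a four-component label.
- The ectopic count reported separately would not appear in the composite, so the component counts would not reconcile with it.
- Analyses are run separately in six data sources, and Section 9.6 says that some providers analyse their own data. One programmer could follow Table 5 and another Section 9.3.2, giving different endpoints by source.

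**Working it through.** There is no figure in the plan to reproduce, so the check is first textual and then illustrative.

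**Passages side by side**

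| Place | What it implies for ectopic pregnancies in the composite |
|---|---|
| Section 8.1, Objectives 8 and 9 | Counted as events |
| Section 9.3.2, composite definition | Counted as events |
| Section 9.1, Table 3 | Population is all pregnancies, so included |
| Section 9.2.2, Table 5 | Removed, since only the ectopic outcome is exempt |
| Section 9.7.3, Objectives 8 and 9 | Uses the Table 5 cohort, so removed |

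No other text restores them for the composite.

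**Illustrative size**

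Let *e* be the share of pregnancies that are ectopic and *q* the risk of any other component loss among non-ectopic pregnancies.

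- Composite as defined: *e* + (1 − *e*)*q*
- Composite in the Table 5 cohort: *q*, because ectopics leave both numerator and denominator
- Understatement: *e*(1 − *q*)

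Inputs: *e* is assumed, because the protocol gives no rate. For *q*, 20% is borrowed from Section 9.5.1.1 ("A prevalence of 20% for the composite of select pregnancy loss outcomes (composite of spontaneous abortion and stillbirth"). That figure omits elective terminations, for which the protocol gives no rate.

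| *e* (assumed) | As defined, *q* = 20% | Table 5 | Understatement |
|---|---|---|---|
| 0.5% | 0.005 + 0.995 × 0.20 = 20.4% | 20.0% | 0.4 points |
| 1% | 0.01 + 0.99 × 0.20 = 20.8% | 20.0% | 0.8 points |
| 2% | 0.02 + 0.98 × 0.20 = 21.6% | 20.0% | 1.6 points |
| 3% | 0.03 + 0.97 × 0.20 = 22.4% | 20.0% | 2.4 points |

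The result is not sensitive to *q*. Section 9.5.1.1 cites 15.3% to 30% for spontaneous abortion plus stillbirth. At *e* = 1% and *q* = 30% the understatement is 0.01 × 0.70 = 0.7 points. At *e* = 2% and *q* = 15.3% it is 0.02 × 0.847 = 1.7 points. Adding terminations raises *q* and so shrinks the gap.

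In counts, the plan expects 497 exposed pregnancies at 10% uptake. If that total includes ectopics, 497 × 0.01 ≈ 5 to 497 × 0.02 ≈ 10 exposed pregnancies would drop out, all of them events. At 0.5% to 3% the range is about 2 to 15.

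**Effect on the risk ratio**

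With equal *e* and equal *q* in both groups, the risk ratio is 1.00 under either version. If ectopic risk differed, for example an assumed 2% in exposed and 1% in unexposed with *q* = 20% in both, the composite as defined would give 0.216 / 0.208 = 1.04, while Table 5 would still give 1.00. The exclusion therefore hides any ectopic contribution, but that contribution is small on these assumptions.

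**The case against.** **The intent is clear elsewhere.** Ectopic pregnancy is listed as a component wherever the composite is defined, and Table 3 says all pregnancies. One could read the Table 5 exemption as covering any outcome that counts ectopics. That is probably what the sponsor meant, and it makes this an incomplete parenthesis rather than a deliberate choice. But Table 5 does not say so, and it is the table from which the cohort will be built.

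**Table 5 may not be the main source of loss.** Step 2 of Section 9.2.2 already excludes pregnancies whose conception date cannot be established, and Section 9.3.3 notes that gestational age is seldom available for ectopic pregnancies. Some ectopics will therefore be gone before Table 5 applies, and correcting Table 5 will not bring them back. This stands, and it makes the figures above upper illustrations for a given true ectopic rate. It does not apply equally everywhere: the Table 17 notes describe a fixed gestational age assigned in Carelon when no code is found.

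**The exposed row is unclear.** In the text as read, the ectopic line in that row follows the inclusion heading with no exclusion heading. The row spans a page break, so this may be an extraction artefact, and the wording makes sense only as an exclusion. No one-sided bias should be inferred from it.

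**The scope is narrow.** The primary pregnancy-loss outcome consists of spontaneous abortion and stillbirth only, the meta-analysis covers primary outcomes only, and ectopic pregnancy is still reported separately. All of this is correct and limits the weight of the point, but it does not remove the contradiction.

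**Conclusion.** The point holds. As written, Table 5 leaves a defined component of the foetal-loss composite structurally empty in both groups, and nothing else in the protocol corrects it. The understatement of absolute risk is about 0.8 to 1.6 percentage points if 1% to 2% of pregnancies are ectopic and other loss is about 20%. Both inputs are assumptions, and the conception-date exclusion would reduce the effect. The distortion of the risk ratio is nil if ectopic risk is equal across groups and small otherwise. Only the composite in secondary Objectives 8 and 9 is affected. It should be corrected, but it does not threaten the primary conclusions.

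**What to change.** In both pregnancy rows of Table 5, state that ectopic pregnancies are excluded except for the ectopic pregnancy outcome and the composite of foetal loss, and make sure the line sits under an exclusion heading in the exposed row.

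Align Table 3 by noting which outcomes use all pregnancies (ectopic pregnancy, composite of foetal loss) and which use non-ectopic pregnancies (the remaining outcomes of that cohort). After this change the event counts will reconcile, but the component risks will not sum exactly to the composite risk because the denominators still differ; a table footnote should say so. It would also help to report how many ectopic pregnancies are lost at Step 2 for want of a conception date.

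The alternative, deleting ectopic pregnancy from the composite wherever it is defined, would also restore consistency, but it changes the endpoint.

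The cost is a one-line text correction plus a table note, with no effect on sample size or timelines if made before the cohorts are programmed.

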9.3 Variables

Variables used in this study are subdivided into exposure of interest (see Section 9.3.1), outcome parameters of interest (see Section 9.3.2), and participants characteristics and potential confounding variables and risk factors (see Section 9.3.3).

In this protocol, the International Statistical Classification of Diseases and Related Health Problems, 10th Revision (ICD-10) has been used as the coding system for the definition of the outcome variables, other relevant diagnoses, and procedures.

International non-proprietary names are used as nomenclature for prescription drugs. World Health Organisation's (WHO) Anatomical Therapeutic Chemical (ATC) classification system has been used for all prescription drugs in this protocol. The ICD-10 and ATC codes used in this protocol for variable definitions will be amended to the relevant coding systems as appropriate for the respective data sources and will be provided in the statistical analysis plan (SAP).

[Appendix D. Exemplar Codelists](#) provides an exemplar list of codes for exposure variables, outcome variables, and other variables for which either ATC codes and/or ICD-10 are used. The list of codes will be finalised in the SAP.

9.3.1 Exposure definition and measures

Study drugs

Exposure to anifrolumab and other SLE SOC drugs (see [Table 19](#)) will be ascertained from recordings of outpatient visits, procedures, prescriptions, prescriptions dispensed at community pharmacies, or insurance claims registrations, as available in the different data sources.

According to the drug indication, anifrolumab is expected to be prescribed as an IV infusion as part of polytherapy (i.e., add-on therapy to other SLE SOC drugs). However, due to the long study duration, the method of administration may change over time. Therefore, for the main analysis, the objectives will be evaluated in pregnancies exposed to anifrolumab in the polytherapy setting, regardless of administration route.

Despite that anifrolumab is indicated as an add on therapy, it is possible that some patients, either due to incomplete information on medication or off-label use, anifrolumab may be observed to have monotherapy. Therefore, a sensitivity analysis including anifrolumab exposure both as monotherapy and polytherapy will be performed. Details of this sensitivity analysis is provided in [Section 9.7.5](#).

Drug classes used in SLE SOC include antimalarials, glucocorticoids, immunosuppressants (both synthetic and biologic), immunoglobulins and plasmapheresis ([43](#), [55](#), [71](#)) ([Table 19](#)).

Co-medications ([43](#), [55](#)) (prescription drugs other than SLE SOC drugs in [Table 19](#)) are reported in [Table 27](#).

Classification of in utero exposure to SLE drugs and co-medications

The **window of clearance** is defined as 5 times the terminal half-life of the drug for SLE SOC and/or co-medication¹⁰, or, in certain cases, such as biologics, time for concentration to fall below the lowest level of quantification (LLOQ) for 95% of patients. LLOQ is 16 weeks for anifrolumab (2), 14 weeks for belimumab (60) and 15 weeks for rituximab (84).

Particular care will be taken in the definition and classification of *in utero* exposure of the offspring (i.e., through treatment received by the mother during or in the 16 weeks before pregnancy for anifrolumab, 14 weeks for belimumab, 15 weeks for rituximab, and 5-half-lives for other SLE SOC drugs).

Exposure to SLE SOC and/or co-medication (excluding biologics) will be assessed from LMP2 until end of first trimester for the outcome of MCM, and from LMP2 until end of pregnancy for all other outcomes. A look back period of 5-half-lives of relevant drugs will be considered. This is to account for prescription/dispensations/administrations prior to LMP2 that gave rise to *in utero* exposure of the offspring.

SLE SOC and/or co-medications are assumed to be continued throughout pregnancy. It is common for SLE to be more active during pregnancy with a high prevalence of flares (11, 12, 28, 63, 67). The risk of adverse outcomes among pregnant women who have SLE is related to disease severity (e.g., involvement of the kidneys) and activity during pregnancy (29, 39), thus it is expected that SLE treatment would occur even in pregnancy. A sensitivity analysis accounting for actual use of SLE SOC during pregnancy is presented in Section 9.7.5.

Exposure to anifrolumab will be assessed from LMP2 until end of the first trimester for the outcome of MCM, and from LMP2 until end of pregnancy for all other outcomes (see Section 8.1), or until censoring, regardless of duration of exposure. Considering anifrolumab window of clearance (16 weeks, see definition above), all patients who receive prescriptions/dispensations/administrations of anifrolumab in the 16 weeks prior to LMP2 or during pregnancy will be considered exposed (2).

Offspring whose mother had no anifrolumab prescription/dispensations/administration in the 16 weeks prior to LMP2 or during the first trimester for the outcome of MCM, or during pregnancy for all other outcomes, will be considered unexposed.

Although, the foetus is most at risk during the period of organogenesis (i.e., during the first trimester of pregnancy), exposures during other gestational time periods may also be associated with adverse outcomes (e.g., spontaneous abortion, stillbirth, or other pregnancy complications). The identification of critical windows of exposure *in utero* provides clues to possible mechanisms of the pregnancy loss and provides guidelines for protection of the foetus. An exploratory analysis focusing on the effect of *in utero* exposure to anifrolumab in different trimesters of pregnancy on the

¹⁰ The respective half-lives of SLE SOC and co-medications will be provided in the SAP.

occurrence of select pregnancy loss outcomes (composite of spontaneous abortion and stillbirth will be assessed:

- **Exposed during pregnancy by trimesters** – *in utero* exposed to anifrolumab will be determined for each pregnancy trimester (dichotomous variables) and combined into a pattern of exposure by trimester (Table 6). The exposure by trimester will be defined as:
 - in each trimester, offspring whose mother had at least one prescription/dispensations/administration of anifrolumab leading to an exposure period overlapping with a specific trimester(s), will be classified as exposed (yes/no) (Table 6);
 - offspring whose mother had no anifrolumab prescription/dispensations/administration in the 16 weeks (anifrolumab window of clearance) prior to LMP2 or during all pregnancy, with the assumption of continuing treatment with SOC, will be classified as non-exposed (yes/no) (Table 6).

Table 6: Maternal exposure status by trimester, offspring *in utero* exposed to anifrolumab (polytherapy) vs offspring *in utero* exposed to SLE SOC

Exposed group				Comparator group		
1 st trimester	2 nd trimester	3 rd trimester		1 st trimester	2 nd trimester	3 rd trimester
anifrolumab (+ SOC)	SOC ¹	SOC ¹	VS	SOC	SOC ¹	SOC ¹
anifrolumab (+ SOC)	anifrolumab (+ SOC)	SOC ¹	VS	SOC	SOC	SOC ¹
anifrolumab (+ SOC)	anifrolumab (+ SOC)	anifrolumab (+ SOC)	VS	SOC	SOC	SOC
SOC	anifrolumab (+ SOC)	anifrolumab (+ SOC)	VS	SOC	SOC	SOC
SOC	SOC	anifrolumab (+ SOC)	VS	SOC	SOC	SOC

Abbreviations used in the table: SOC, Standard of care; VS, Versus

¹ SOC might not be applicable if pregnancy ends early

Definition of exposure period

Women exposed to anifrolumab during pregnancy are included in the exposed groups regardless of the exposure status before pregnancy. The maximum exposure period is from LMP2 to delivery/birth. The maternal exposure period during pregnancy is not considered to be fixed. This is because pregnancy duration is not exactly the same for all pregnancies (full-term birth is considered between 37 to 42 weeks of gestation). Also, exposure period can end earlier with a censoring event (e.g., elective termination of pregnancy).

The definition of exposure period relies on available information on the date of prescription/dispensation/administration, the expected supply (i.e., package size, the number of packages prescribed/dispensed), and the estimated window of drug clearance (for anifrolumab, the time for concentration to fall below the LLOQ for 95% of patients is 16 weeks from last administration). The exposure period starts on the date when the drug was administered or

prescribed/dispensed (if information on the date of dispensation is not available, the start of the exposure period will be defined based on the date when the prescription was issued). The end date of the exposure period is calculated by adding the estimated window of clearance and expected supply to the prescriptions/dispensations/administrations date (Figure 6).

[figure not shown]

Figure 6: Anifrolumab exposure period

